This study is a randomised, double-blinded, superiority clinical trial with six parallel groups. The hypothesis tested to evaluate two early childhood tooth caries treatment methods with two different application protocols, comparing a placebo, will be performed at the Rīga Stradiņa University's (RSU) Institute of Stomatology Children's Dentistry department.

Participants

According to the AAPD's (American Academy of Pediatric Dentistry) definition of severe early childhood caries (S-ECC) is a condition when a child up to 3 years old has at least one caries damage without cavitates and from 3 to 5 years old with at least one caries damage with cavitates (AAPD). Every week approximately 15 children ages 2-6 years-old with multiple caries damage seek consultations about the possibility to receive planned tooth treatment under general anaesthesia (GA) at the RSU Institute of Stomatology. After confirmation of the diagnosis, the children are put on a waiting list for treatment, which lasts 12 months. These children are offered to participate in this study, while they wait for rehabilitation with general anaesthesia. Every day approximately 10 children arrive that are at an age to be included in the study, with acute pain or an infection. They are also given the opportunity to participate in the study, if they conform with the criteria. As a result, the patient's involved in the study have common characteristics: multiple caries damage with cavities (indicating restorative treatment); a high level of caries risk factors; possible difficulties with behavioural control. To bring the study's sample patients as close as possible to the overall children's population, participants will be included according to defined criteria.

Inclusion criteria:

- children aged 2-6;
- have at least one active caries damage with cavitates (comply with the diagnosis of S-ECC);
- wish to participate in the study;
- parents agree to participation in the study and sign a consent form.

Exclusion criteria:

- the child arrives with an adult who doesn't have the right to sign a consent form, and the person responsible for the child cannot be present;
- chronic or serious acute general illness;
- in the last month has used medications, that could affect the secretion of saliva;
- previously received treatment with products that have a high level of fluoride concentration.

Sample size calculation

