1. arresting of the lesions – restorative treatment may no longer be necessary, but, in case the child are waiting for treatment under GA, they will not lose their place, and restorative treatment will be offered if parents will still want it because of esthetic reasons;
2. staining of the teeth – when lesion is arrested, damaged dental enamel and dentine often change colour, become darker, and the treatment methods can facilitate that (especially SDF), and therefore the teeth can become unattractive;
3. unpleasant taste during the procedure.

[figure not shown]

Fig 2. Flow chart of the clinical trial.

If the parents agree to the study, they will be assigned an appointment with one of two calibrated examiners, who will again explain the study and in whose presence, they will sign the informed consent form. If the parents for some reason decide not to participate, they can withdraw without any negative consequences. The calibrated specialist will perform a damage progression and activity register (ICDAS, Nyvad criteria) and draw lots with a closed envelope, of which group the patient will be included in (with a color code).

The patient, with information about their group's color goes to another office, where one of four trained dentists and assistants will be working (Intervention staff - IS). They will be informed about the medication to be used in each of the groups. The corresponding treatment method will be applied, and the child will be asked to describe their feelings during the procedure by using visual

analogue scale (VAS), the next visit will be set according to the group's corresponding protocol. On all future treatment appointments, the patient will only see the dentists and assistants of IS.

After the last application foreseen in the protocol, the patient will be assigned a control appointment, which will be 12 months after the first examination. During the control appointment one of the calibrated examiners will perform a documentation of stage and activity of carious lesions, not knowing which treatment had been applied. The questionnaires for the parents and children about their satisfaction with the appearance of their teeth will be applied.

Interventions

Patients who agree to participate in the study, will be randomly placed into one of six groups:

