4. **WP4** Clinical trial. **The objective of WP4** is to perform the clinical trial according to an established protocol and the highest ethical standards with the primary aim of finding out which high-concentration fluoride application method and which application protocol more effectively protects pre-school children from complications arising from early childhood dental caries. Secondary objectives are to evaluate at which stage of development (cariou lesions) the methods are the most effective; which fluoride application method and protocol is more effective in arresting non-cavitated and cavitated cariou lesions in preschool children; how satisfied are parents and patients with SDF and Tiefenfluorid application procedures and side-effects (staining) and what are the costs and cost-effectiveness of each method and application protocol.
 1. Enrolment of patients in the study. General staff will offer suitable patients the chance to register for the procedures. A calibrated examiner (postdoctoral researcher) will inform parents about all details of the study. If the offered is accepted, parents sign the informed consent form.

2. Initial examination and interviewing of enrolled patients and their parents by a calibrated examiner (postdoctoral researcher).
3. Random allocation in six intervention groups. This will be done by a calibrated examiner (postdoctoral researcher) using six closed envelopes containing colour codes.
4. Performing interventions according to the protocol of each study group. Those interventions will be done by Intervention Staff (IS) - four trained postgraduate students and assistants (dental hygiene students).
5. Performing and documenting emergency treatment during the follow-up period. Done by trained general staff on a daily basis according to patient needs. Registration will be done using a pre-prepared form.
6. Follow-up examination. Done by calibrated examiner (postdoctoral researcher).

Deliverables of WP4

D4.1 Enrolment registration form.

D4.2 Signed informed consent forms.

D4.3 Initial patient examination forms (including parent questionnaire).

D4.4 Intervention registration forms (including Visual Analogue Scale [VAS] of patient satisfaction).

D4.5 Emergency treatment forms (including VAS of patient satisfaction).

D4.6 Follow-up examination forms (including VAS of patient acceptance and Likert scale questions of parents acceptance).

Milestones of WP4

MS4.1 Meetings about enrollment, randomization and allocation.

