 - a. Patients received treatment outside the RSU Institute of Stomatology – every case will be analysed separately; if, for any reason, the patient attended a dentist who was not trained for the study (in the Institute of Stomatology or in another dental clinic), the recordings of treatment performed will be analysed – if there is no doubt regarding the information gained and if the treatment was done according to the guidelines used in the study, the patient will be kept in the study. In case of doubt, he/she will be excluded from analysis. This increases the risk of loss of follow-up, but it is important that we are sure about the impact of the treatment performed. Evenmore, as described above, we will include more patients than required to assure the study power even after some losses of follow-up.
 - b. Blinded research team members are informed about colour codes of the treatment groups – we will consider changing the person in case the this knowledge leads to performance or detection bias. We also will include as less personal as possible and the most motivated colleagues to avoid such errors.
 - c. Patients find out which treatment group they have been assigned to– it is possible that the groups which receive SDF “feel” the treatment to be more effective because of the staining side effect. However, we are not yet sure how important this effect will be, as all of those children have tooth damage which includes some colour change of the lesions. It is also known that arrested lesions tend to become darker even without the application of any agent. We will be able to address this risk by evaluating the patient and parent satisfaction in different treatment groups.

Infrastructure

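### Concealment and assessor blinding are inadequately protected: the examiner role that enrols and scores baseline also draws the colour-coded group and, under WP4, does the 12-month examination

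*Protocol*

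**What the plan says.** Study design and settings calls the study a "randomised, double-blinded, superiority clinical trial with six parallel groups" and does not list the blinded roles.

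Under Randomization, allocation and blinding, parents sign consent in front of one of two calibrated examiners. That examiner records lesion stage and activity and will then "draw lots with a closed envelope, of which group the patient will be included in (with a color code"). The child takes the colour to another office, where the intervention staff work. Of these staff the section says: "They will be informed about the medication to be used in each of the groups". They alone see the child at later treatment visits. At 12 months one of the calibrated examiners scores the lesions and is said not to know the treatment.

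WP4 names one role, the calibrated examiner (postdoctoral researcher), for informing parents, the initial examination and the allocation: "This will be done by a calibrated examiner (postdoctoral researcher) using six closed envelopes containing colour codes". Task 6 reads: "Follow-up examination. Done by calibrated examiner (postdoctoral researcher").

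Risks 2b lists this hazard: "Blinded research team members are informed about colour codes of the treatment groups". The response is to consider changing the person if bias results, and to use few, motivated staff. Risks 2c accepts that patients may discover their group through SDF staining.

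**The concern.** The person who decides whether a child enters should not control the draw, and the person who scores the outcome should not know the group. Here one role enrols, scores baseline, draws and, by WP4, scores at 12 months. Two weaknesses follow.

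- **Concealment.** It depends on the enrolling examiner's own handling of the envelopes. The protocol fixes a specific procedure with six envelopes but describes no generated sequence, numbering, log or independent custody. Nothing described prevents a second draw.
- **Assessor blinding.** The colours are constant through the trial, so one colour-to-treatment link decodes a whole arm. The introduction says SDF stains teeth black. An examiner who remembers or can look up the colours could make that link from a few stained children.

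At stake is detection bias in lesion activity (active/non-active and Nyvad) and ICDAS progression. These need judgement and are secondary outcomes. There is also a smaller opening for selection at entry.

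**Working it through.** The protocol states no figure on this point to reproduce. The check sets the sections side by side and then works out what six envelopes imply.

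**Who does what**

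| Step | Randomization section | WP4 |
|---|---|---|
| Consent | one of two calibrated examiners | calibrated examiner (postdoctoral researcher) |
| Baseline scoring | calibrated specialist | same role |
| Draw of colour | the same specialist, closed envelope | same role, six closed envelopes |
| Treatment | intervention staff, who know the products | intervention staff |
| 12-month scoring | one of the calibrated examiners, treatment unknown | same role as the draw |

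The two accounts agree that the baseline examiner draws. They differ on follow-up: the randomization section allows either examiner, and WP4 names the role that drew. Neither requires the follow-up examiner to be someone other than the drawer. That the examiner sees the colour is the natural reading of drawing a colour-coded lot, but it is not stated outright.

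**Inputs for the arithmetic:** 6 groups, 420 children, 70 per group, 30% loss, 49 needed per group at the end (Sample size calculation; Risks 1b).

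**Reading A: six envelopes used up, then refilled (no replacement).** With k envelopes left, the chance of guessing the next colour is 1/k.
- Mean chance = (1/6)(1/6 + 1/5 + 1/4 + 1/3 + 1/2 + 1) = 2.45/6 = 0.408, against 1/6 = 0.167 for an unpredictable draw.
- The sixth draw of every block is certain: 420/6 = 70 children.
- Group sizes stay at 70.

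**Reading B: envelope returned after each draw (replacement).** Every draw has chance 1/6, so nothing is predictable, but group sizes are multinomial(420, 1/6).
- SD of one group = √(420 × 1/6 × 5/6) = √58.33 = 7.64.
- Simulated smallest of six groups: mean 59.6, median 60; probability that it is below 60, 0.45.
- After 30% loss: 60 × 0.70 = 42, against the 49 required.

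A and B exclude each other. The trial cannot have both the 41% and the SD of 7.6. The protocol does not say which applies.

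**The case against.** - **The envelopes are closed, hold colours rather than product names, and are drawn after consent and the baseline record.** The key is described as given to the intervention staff in another office. This stands. A reader might infer that allocation is not concealed at all, but the documents show only weak protection. Guessing a colour is not guessing a treatment unless the key leaks.
- **The randomization section says the follow-up examiner does not know the treatment.** This stands as a stated intention. It conflicts with the role named in WP4, and no safeguard backs it.
- **Staining can hardly drive selection at entry.** Largely right. Examiners do not see children at treatment visits, so they would normally meet stained teeth at 12 months. With about 15 general-anaesthesia referrals a week, 420 children take 420/15 = 28 weeks if all join, or 56 weeks if half do (uptake is an assumption). Most enrolment could precede the first follow-up.
- **Decoding by stain is limited.** It would reveal the two SDF colours, not Tiefenfluorid against placebo. The stain on the child's own teeth also stays visible however the envelopes are handled. Both stand.
- **Families know their schedule, but each schedule has its own placebo group.** This stands. A reader might infer that visit timing unblinds parents, but it does not separate active from placebo within a schedule.
- **The examiner-scored outcomes are secondary.** This stands. The primary outcomes are pain history, abscess history and extractions; the protocol does not say who reports the pain history.
- **The imbalance under reading B costs little.** Fair. A group of 42 against an average of (294 − 42)/5 = 50.4 in the others has a harmonic mean of 2/(1/42 + 1/50.4) = 45.8, against 49.
- **Risks 2b also plans few, motivated staff.** True, but this does not keep the colour from the person who draws it.

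**Conclusion.** The point holds in limited form. Concealment and assessor blinding are inadequately protected because drawing is not separated from enrolling and, under WP4, not from outcome scoring. Neither failure is demonstrated. The size depends on an unstated detail: either a 41% mean chance of guessing the colour with 70 certain draws, or unpredictable draws with a group-size SD of 7.6 and a smallest group of about 60. The exposure falls mainly on caries activity and progression. It assumes that the drawing examiner sees the colour, can still link it to the child at 12 months, and does the follow-up.

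A reader might conclude that the double-blind label fails because the examiner sees a colour. That does not follow, since a colour is not a treatment. The label is unsafe for other reasons: the intervention staff know the product, the blinded roles are not named, and SDF staining can reveal the arm to examiner and parents. The direction of any bias cannot be read from the documents.

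The change should be made before enrolment, because a compromised draw cannot be repaired afterwards.

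**What to change.** 1. Have the university's biostatistics support, already listed under Infrastructure, generate a blocked allocation list and prepare 420 sequentially numbered, opaque, sealed envelopes.
2. Have the intervention staff open the next envelope in the treatment office once the baseline form is complete. The examiner never sees the colour or the visit schedule. Amend WP4 task 3 and the randomization section accordingly.
3. Make the randomization section and WP4 task 6 agree on who does the 12-month examination.
4. Replace the double-blind label with a list of roles that are and are not blinded. State that the intervention staff know the product and that SDF staining may unblind the examiner and parents whatever the envelope procedure.

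The cost is protocol wording and one set of prepared envelopes. No extra staff or visits are needed. The change removes the colour route to unblinding and controls group sizes; it does not remove unblinding by visible stain.

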- 4) the level and development of the caries damage and activity (ICDAS, Nyvad criteria).

Outcome measures:

- I. Primary outcome measures:
 - A. Pain history during the observation period, assessed as Yes/No at 12 months follow-up visit.
 - B. Abscess history during the observation period, assessed as Yes/No at 12 months follow-up visit.
 - C. The number of newly extracted or otherwise surgically treated teeth during the observation period, assessed as a number of extracted teeth during the last year at 12 months follow-up visit.
- II. Secondary outcome measures:
 - A. The change in the overall activity of caries as Active/Non-active, assessed at 12 months follow-up visit.
 - B. The progression and change of activity of every lesion, assessed by ICDAS (for progression) and Nyvad (for activity) criteria, at 12 months follow-up visit.
 - C. The parent’s satisfaction with the way their children’s teeth look, assessed by questionnaire, asking: “Are you satisfied with the way your child’s teeth look?”

- and “Would you agree to repeat the treatment procedure used?”, both measurements in 5-point Likert scale, assessed at 12 months follow-up visit.
- D. The child’s satisfaction with their teeth, measured by the visual analogue scale (VAS) with 3 points - happy, not sure, sad, assessed at 12 months follow-up visit.
 - E. The child’s feelings during the treatment, measured by the modified Wong-Baker scale with 3 options - no hurt, hurts a little, hurts a lot), assessed during every appointment (depending on treatment group can be assessed at baseline, 1, 2, 3 weeks and 12 months; or at baseline, 6 and 12 months).
 - F. The direct costs of the treatment and the cost-effectiveness, calculated as EUR spent per treatment protocol; EUR per prevented major complications (in patient-level - pain, abscess, extraction) and EUR per prevented minor complications (in tooth-level - progression of caries lesion), the calculation will be made at 12 months follow-up.
 - G. The treatment method’s undesirable side effects, assessed by parents’ questionnaire at the 12 months follow-up visit.

Statistical analysis

Data will be digitized, by entering in an ad-hoc form in the Google Docs programme. Further the data will be exported cvs (comma separated values) to an archive. Missing data will be eliminated from the analyses, marking them NA.

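### The child's rating of hurt at the application visits (II.E) appears to be collected by staff who know the product, and the stated examiner blinding does not cover it

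*Protocol*

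**What the plan says.** The design statement reads: "This study is a randomised, double-blinded, superiority clinical trial with six parallel groups".

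Under Randomization, allocation and blinding, the child "goes to another office, where one of four trained dentists and assistants will be working (Intervention staff - IS"). Of these staff the protocol says: "They will be informed about the medication to be used in each of the groups". It continues: "The corresponding treatment method will be applied, and the child will be asked to describe their feelings during the procedure by using visual" analogue scale. For later visits: "On all future treatment appointments, the patient will only see the dentists and assistants of IS".

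The same section states one assessor safeguard, for the control appointment at 12 months: "one of the calibrated examiners will perform a documentation of stage and activity of carious lesions, not knowing which treatment had been applied".

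Outcome measures, item II.E, defines the secondary outcome: "The child’s feelings during the treatment, measured by the modified Wong-Baker scale with 3 options - no hurt, hurts a little, hurts a lot"). It is taken at every appointment: baseline, 1, 2 and 3 weeks and 12 months under one schedule, and baseline, 6 and 12 months under the other.

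The WP4 deliverables list "D4.4 Intervention registration forms (including Visual Analogue Scale [VAS] of patient satisfaction").

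**The concern.** The staff who apply the product have to know what it is. The question is whether they also have to collect the child's opinion of it. As written, the two tasks fall in the same room and the same step, and nothing separates them.

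II.E is reported by children aged 2 to 6, whom the Participants section describes as possibly having behavioural difficulties. At that age an adult normally has to explain the scale and sometimes has to interpret the answer. If the explaining or interpreting varies with the known product, the variation becomes a difference between arms, or masks one. Randomisation gives no protection, because this happens after allocation.

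II.E is the measure taken at the time of application, and it bears on the WP4 secondary objective about how satisfied parents and patients are with the SDF and Tiefenfluorid application procedures. An answer distorted on the day cannot be recovered later.

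**Working it through.** The point rests on reading the provisions together. The protocol gives no figure to reproduce.

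1. **Who knows the product.** The sentence on being informed of the medication follows directly on the description of the intervention staff, who are its natural antecedent. They are unblinded by design.
2. **Who is present when the child is asked.** Application and rating share one sentence and one office. At later treatment appointments the child sees intervention staff only. No other person is described as attending to collect the rating.
3. **Where the answer goes.** D4.4 puts a child scale on the intervention registration form, and WP4 task 4 assigns the interventions to the intervention staff. The labels differ: a visual analogue scale of feelings in the blinding section, a modified Wong-Baker scale in II.E, and a satisfaction scale in D4.4. Treating them as one instrument is an inference.
4. **What the stated blinding covers.** It covers the examiner's record of lesion stage and activity at 12 months. It is not stated for any application visit.
5. **What the Risks section covers.** Item 2b deals with blinded team members learning the colour codes. Item 2c deals with patients learning their group. Neither deals with ratings collected by staff who are unblinded by design.
6. **Whether the 12-month rating could substitute.** Under Interventions, applications end at six months in one schedule and at the fourth weekly visit in the other. A 12-month rating is listed, but no application is scheduled for that visit, so it does not replace the ratings taken on the day.

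**Scale, by assumption only.** The protocol gives no expected rate of hurt and no basis for a recording shift. To show how the risk would translate, assume a true rate of any hurt of 30% with both products. Assume also that handling lowers the recorded rate for one product to 25% or to 20%. Planned enrolment is 70 per group, or 2 × 70 = 140 per product with the two schedules pooled. For a two-sided 5% test, z = (p1 − p2) / √[(p1(1 − p1) + p2(1 − p2)) / n], and the chance of significance is Φ(z − 1.96) + Φ(−z − 1.96).

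| Recorded rates | n per arm | z | Chance of a false significant difference |
|---|---|---|---|
| 30% v 25% | 140 | 0.05 / √(0.3975/140) = 0.94 | 15.5% |
| 30% v 25% | 70 | 0.05 / √(0.3975/70) = 0.66 | 10.2% |
| 30% v 20% | 140 | 0.10 / √(0.37/140) = 1.95 | 49.4% |
| 30% v 20% | 70 | 0.10 / √(0.37/70) = 1.38 | 28.0% |

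These figures include the nominal 5%. For the five-point shift the excess is therefore 15.5 − 5 = 10.5 points at 140 per arm and 10.2 − 5 = 5.2 points at 70. The ten-point shift needs one in three hurt answers (10/30) to be softened for one product only. With no shift, the chance stays at the nominal 5%.

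**The case against.** The case on the other side has real substance.

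- **The asker is not named.** The sentence is passive. This stands: collection by the intervention staff is a firm inference, not a stated fact.
- **The child answers, not the staff.** This also stands. The staff score nothing, so the only route is prompting, helping or recording that differs by product. Young age, behavioural difficulty and a coarse scale apply equally in all six groups. By themselves they add noise or a common shift, not a product difference. The protocol gives no reason to think operators favour one product.
- **The instrument may already be standardised.** WP2 plans to create and validate the questions and scales, WP3 trains the intervention staff, and the Ethics section refers to an attached children's questionnaire that is not available here. A fixed question may exist. That would narrow the route through wording, but it would not blind the person who asks and records.
- **Other measures serve the same objective.** Items II.C, II.D and II.G bear on satisfaction and side effects at 12 months, and II.E itself has a 12-month rating. This limits the importance of the point, but none of these records the experience at the time of application.
- **A parent is not a neutral helper.** Parents are warned of unpleasant taste and of staining, especially with SDF, and may guess. This stands as a drawback of the remedy. A guess is still weaker than the operator's certain knowledge.

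A reader might infer that II.E is shown to be biased, that the double-blind claim fails for the trial as a whole, or that only first-application ratings can be trusted. The protocol supports none of these. No differential handling is documented. The primary outcomes are assessed at the 12-month visit. Dropping the repeat ratings would discard planned data on how the application schedules are tolerated.

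**Conclusion.** The point holds as a gap in the protection of one secondary outcome. At the application visits, II.E is most naturally read as elicited and recorded by staff who know the product and have just applied it, and the text describes no safeguard. The conclusion rests on two inferences: that the unnamed asker belongs to the intervention staff, and that the child scale on the intervention form is the II.E rating. It does not extend to the primary outcomes or to the lesion examination at 12 months.

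The consequence is a possible bias of unknown direction and size. The 10% to 49% range in the table follows entirely from assumed rates and shifts. It shows how sensitive the comparison would be and is not an estimate for this trial.

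**What to change.** In Randomization, allocation and blinding, and on form D4.4, state that at every application visit:

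- the child marks a three-option card bearing one fixed printed question, away from the operator and with the accompanying adult;
- the adult is not told the product;
- the card carries only the study number and is sealed in an envelope without being seen by the intervention staff.

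Use the same name for the instrument in the blinding section, II.E and D4.4. Keep all scheduled ratings in the analysis.

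The cost is a printed card, an envelope and a short protocol edit, with no extra staff or visits. The downside is that the adult may influence the mark or may guess the product from taste or, at repeat visits, from staining.

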1. The first placebo group – placebo varnish application twice with a six-month interval and a recommendation to brush teeth with a toothpaste containing fluoride (F content of at least 1000 ppm);
2. The second placebo group – placebo varnish application four times with a week's interval and a recommendation to brush teeth with a toothpaste containing fluoride (F content of at least 1000 ppm);
3. The first SDF group – Riva Star SDF (35-40% silver fluoride, 15-20% ammonium) application twice with a six-month interval and a recommendation to brush teeth with a toothpaste containing fluoride (F content of at least 1000 ppm);
4. The second SDF group - Riva Star SDF application four times with a week's interval and a recommendation to brush teeth with a toothpaste containing fluoride (F content of at least 1000 ppm);
5. The first Tiefenfluoride group – Tiefenfluoride (0,4% $\text{CuSiF}_6 \times 6 \text{H}_2\text{O}$, 10,9% $\text{MgSiF}_6 \times 6 \text{H}_2\text{O}$, 0,1% NaF, 9,6% $\text{Ca}(\text{OH})_2$) application twice with a six month interval and a recommendation to brush teeth with a toothpaste containing fluoride (F content of at least 1000 ppm);
6. The second Tiefenfluorid group - Tiefenfluorid application four times with a week's interval and a recommendation to brush teeth with a toothpaste containing fluoride (F content of at least 1000 ppm);

The goal of the treatment is to stop the progress of the existing damage progress and avert the formation of new damage; caries tissue removal will not be performed; the products will be applied to dried teeth.

For ethical reasons, the negative control group will not be used – in each of the study’s groups the parents (direct caregivers) will be given advice about tooth cleaning and diet, using motivational intervention principles and recommending brushing teeth with toothpaste that contains fluoride (at least 1000 ppm), which is defined as non-restorative caries treatment and which has also proven its effectiveness in stopping caries damage.

Outcome variables

Patients will be examined at the baseline and at 12 months.

The patient’s primary examination will determine the following parameters:

- 1) general information about the child (birth date, gender, medical health history);
- 2) hygiene and dietary habits (frequency of brushing teeth; are teeth cleaned by the child or by parents; the fluoride concentration in toothpaste);
- 3) plaque (visible/invisible);

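### Brushing and diet advice, which the protocol calls effective, appears to be given after allocation by staff who know the product, so performance bias is a risk

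*Protocol*

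**What the plan says.** The Interventions section of the protocol explains that, for ethical reasons, no group goes without care. Parents in each group "will be given advice about tooth cleaning and diet, using motivational intervention principles and recommending brushing teeth with toothpaste that contains fluoride". The protocol then characterises this advice as something "which is defined as non-restorative caries treatment and which has also proven its effectiveness in stopping caries damage".

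The recommendation is also part of each arm's definition. The first placebo group, for example, is defined as "placebo varnish application twice with a six-month interval and a recommendation to brush teeth with a toothpaste containing fluoride", and the other five definitions have the same second half.

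Under Work packages, WP4, task 4 is "Performing interventions according to the protocol of each study group", and it goes to the Intervention Staff (four postgraduate students and their assistants). Of these staff the section Randomization, allocation and blinding says: "They will be informed about the medication to be used in each of the groups". It adds: "On all future treatment appointments, the patient will only see the dentists and assistants of IS".

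Study design and settings calls the trial double-blinded.

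**The concern.** The trial compares products that are applied on top of a common background of advice. The comparison is clean only if that background is the same in all arms. By the protocol's own account the advice works, so it cannot be dismissed as too weak to matter. It follows a motivational approach, which depends on the person giving it and is adapted to the family. Someone who knows that a high-risk child is receiving placebo may put more effort into the conversation, or less.

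The primary outcomes are pain, abscess and extractions over 12 months. If home care differed by arm, these could differ for reasons unrelated to the product. Extra effort in the placebo arms would hide a product effect, and extra effort in the active arms would mimic one. Counselling differences that nobody recorded cannot be corrected in the analysis, so this is a matter of trial conduct and not one for a statistical analysis plan.

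**Working it through.** The document gives no effect size for the advice, so no arithmetic applies. The check sets the statements side by side.

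1. **Is the advice active?** Yes, by the protocol's own words: "which is defined as non-restorative caries treatment and which has also proven its effectiveness in stopping caries damage" (Interventions).
2. **Does it belong to the arm's treatment?** The brushing recommendation does: it appears in all six group definitions (Interventions). The diet part appears only in the general paragraph that follows them.
3. **Who carries out the arm's treatment?** The Intervention Staff (WP4, task 4).
4. **Is that before or after allocation?** After. WP4 lists the examiner's initial examination and interview as task 2, random allocation as task 3 and the interventions as task 4.
5. **What do these staff know?** The product used in each group: "They will be informed about the medication to be used in each of the groups". They are also the only staff whom the child sees at later treatment visits.
6. **Is the advice fixed in form?** Not in the text. No script, number of sessions, named deliverer or record of delivery is given. WP3 describes the training of the Intervention Staff in terms of treatment methods and does not mention the advice.
7. **Does a stated safeguard cover this?**
   - Risks, item 2b, deals with blinded team members who learn the colour codes. The Intervention Staff know the product by design.
   - The examiner who does not know the treatment at 12 months protects the assessment. That does not help if home care really differed.
   - The follow-up form repeats the risk-factor questions (WP2, D2.5). It could reveal a difference in habits but cannot prevent one.
8. **Which comparisons are exposed?**
   - *Product with placebo, and product with product, on the same schedule.* The number of visits is equal, and knowledge of the product can act directly.
   - *Four weekly applications with two applications six months apart, same product.* The product is the same on both sides, so knowing it does not directly separate the arms. If advice accompanies each application, however, families on one schedule hear it four times within the first weeks, and families on the other hear it twice, six months apart. Which application protocol protects better is part of the primary aim in WP4.

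Steps 2 to 5 together place the brushing recommendation after allocation and with unblinded staff. That is an inference from two sections and not a statement in either.

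**The case against.** The strongest reply is that the protocol never says who gives the advice. The sentence is in the passive. The account of the treatment visit (Randomization, allocation and blinding) covers application of the product, the child's rating and the next appointment, and mentions no counselling. The examiner records hygiene and diet habits at baseline and interviews the parents before allocation, so advice from the examiner at that point is compatible with the text. The flow chart and the attached forms were not available in the copy read and might show where the advice sits. All of this stands, and it is why delivery by the Intervention Staff is put here as the natural reading and not as fact.

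It can also be said that the recommendation is worded identically in all six arms and that the Intervention Staff are trained together for all groups. Identical wording shows the intention of equal advice. It does not secure equal delivery of a motivational conversation by people who know the product.

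A reader might infer that every comparison is biased. The document does not support that. Knowledge of the product does not directly affect schedule comparisons within one product, and a different number of sessions cancels when a product is compared with placebo on the same schedule.

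A reader might also try to put a number on the bias by moving the planned 30% placebo rate. The document does not support that either. Sample size calculation takes the 30% from clinic records of waiting children who had no additional treatment, so it contains no trial advice. A lower rate in the placebo arms could arise with perfectly equal advice. Nor does it follow that uneven effort in the active arms, planned at 10%, would shift the difference by the same amount in the other direction.

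**Conclusion.** The point holds as a risk of performance bias of unknown size and direction. It falls mainly on the comparisons between products and of products with placebo. The schedule comparisons are affected only if the advice is repeated at each application.

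The conclusion rests on two things: reading the arm definitions together with WP4, task 4, so that the Intervention Staff give the advice; and the protocol's own description of that advice as effective. It does not show that advice will in fact differ by arm, and no numerical effect is claimed. It is still more than a missing detail. As written, the plan leaves an active, adaptable co-intervention with unblinded staff after allocation, although a suitable visit before allocation already exists. If the missing flow chart or forms place the advice with the examiner before allocation, what remains is to say so in the text and to standardise any later reminders.

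**What to change.** State in Interventions, and in WP4 task 2, that the calibrated examiner gives the main brushing and diet advice at the baseline interview, before the allocation envelope is opened, with the same content and the same motivational approach for every child. State also that any reminder at application visits uses the same standard material in all six arms, and cover this in the training of the Intervention Staff (WP3). The content of the advice does not change, and no child loses it.

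The cost is a short protocol paragraph, a training instruction and a few more minutes at the baseline visit. The downside is less individual tailoring of reminders later on.
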